For section 3.1: Primary endpoint is greater reductions in pain-related disability. Secondary endpoint is the reduction of pain, anxiety/depressive symptoms, opioid use, and HRQOL.

For section 3.2: There are no safety endpoints in this study.

4. Drugs, Devices and Biologics³**4.1. Manufacturer and name of all drugs, devices and biologics:**

N/A

4.2. Description and purpose of all drugs, devices and biologics:

N/A

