4.3. Regulatory status of all drugs, devices and biologics:⁴

N/A

4.3.1. Drugs or Biologics:

☐ IND Exempt. Explain:⁵ [Click here to enter text.](#)

☐ IND.

4.3.2. Devices:

☐ IDE Exempt. Explain:⁶ [Click here to enter text.](#)

☐ Abbreviated IDE / Non-Significant Risk. Explain:⁷ [Click here to enter text.](#)

☐ IDE / Significant Risk.

4.4. Plans to store, handle, and administer any study drugs, devices and biologics so they will be used only on subjects and be used only by authorized investigators:

N/A

5. Procedures Involved**5.1. Study design:⁸**

A randomized controlled double-blinded trial will be conducted. Families will be randomized to either WebMAP or WebED (education control). 260 children (ages 10-19 years) with CP/ARP and their parents/caregivers (if possible) will be recruited from the INSPPIRE network and pancreatitis-related community organizations such as the National Pancreas Foundation (NPF) and Mission Cure. The intervention phase will last 8-12 weeks. Assessments will occur at baseline (T1), immediately after intervention (2 months; T2), and repeated at 6 months postintervention (T3) to assess maintenance of treatment gains. Primary outcome is pain-related disability (T2, T3).

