Based on our historical data, the estimate of the standard deviation for the primary outcome pain-related disability is approximately 4. We expect a difference of 1.5 between WebMAP and WebED in the mean score of pain-related disability. At the significance level of 0.05, we need 112 subjects per group to have 80% power to detect a difference. Results indicate sufficient power to detect relatively small differences between children receiving WebMAP compared to WebED. Taking into account 10-15% attrition, we will enroll 130 patients per group. Because Aims 2 and 3 employ the LMM regression approach, the power calculation is complicated and requires re-specifying model parameters that are virtually unknown a priori. Therefore, we take a simple approach based on correlation coefficient. Given the sample size of 112 subjects, we have 80% power to detect the correlation of 0.27 between gene (or baseline clinical characteristics) and pain-related disability, at the significance level of 0.05. As the LMM is more efficient, the actual power will be greater. Power to detect correlations between genetic/clinical characteristics and pain-related disability may be lowered depending on the number of community participants enrolled.

11. Withdrawal of Subjects

- 11.1.** Anticipated circumstances under which subjects will be withdrawn from the research without their consent:

The PI may decide to withdraw participants from the study if a family is not able to comply with study procedures or do not understand study instructions.

11.2. Procedures for orderly termination:

If a participant must be withdrawn from all study procedures the study staff would contact the family to explain the cause for study withdrawal and finalized study termination.

11.3. Procedures that will be followed when subjects withdraw from the research, including partial withdrawal from procedures with continued data collection and withdrawal from data/specimen banking:

Full Withdrawal: If a participant must be withdrawn from all study procedures the study staff would contact the family to explain the cause for study withdrawal and finalized study termination.

Partial Withdrawal: If a participant partially withdraws from the procedures, study staff would contact the family to discuss family's interest in participation. If the family is interested, the study procedures will be continued, if the family is not interested, this will be considered a full withdrawal.

12. Risks to Subjects

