Distributions of primary and secondary outcome variables at each time point (and on difference scores between time points) will be examined first with summary statistics and graphical tools. For outcome variables with highly skewed distributions, we will either apply transformation or non-parametric test procedures. Preliminary work will also involve computation of scale reliabilities (e.g., internal consistency using Cronbach's alpha) of all of the self report measures. The RCT analysis will be an intent-to-treat analysis including all randomized subjects. Two-sample t-test will be used to test the difference between the WebMAP group and WebED group in pain-related disability and other outcomes (e.g., anxiety, depression and HRQOL) at baseline, 2 months and 6 months. In the case that the outcome is categorical, the chi-squared test will be used. The pre-post change in pain-related disability will also be assessed within and between groups using one-sample or two-sample t-test. Linear mixed models (LMM) will be further used to compare the change in pain-related disability over time (from baseline to follow-ups) between WebMAP and WebED. The LMM is ideally suited for analysis of repeated measures because it allows for more specific estimation of the correlation structure of the residuals, it efficiently handles unbalanced designs and missing data, without excluding participants or imputing values. The repeated measures of pain-related disability will be treated as the dependent variable. Measurement time, intervention condition, and their interaction will be included in the LMM as covariates. We will include biological covariates of age and sex in all models and will include other demographic and clinical factors, as needed to adjust for potential confounding effects. Fit statistics (e.g., Akaike's Information Criterion) will be evaluated for all models to ascertain the best fit of the correlation structure of the dataset. We will use a computer program, PROC MIXED (SAS v9.3 SAS Institute Inc, Cary, NC) to estimate and test the models with continuous dependent measures. Results will be summarized with the estimates of model parameters and p-values. For a binary endpoint of clinically significant reduction in pain (i.e., achieved 50% or greater reduction in pain intensity), we will employ the generalized linear mixed model (GLMM) to model and compare the changes over time (from baseline to follow-ups) between WebMAP and WebEd. We will use SAS PROC GLMIX, which provides an adaptation to the LMM approach for categorical data.

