
Blood draw and collection will be done by the INSPPIRE 2 study, but will not be done for patients recruited from community organizations who are not participating in INSPPIRE 2. The data we need will be pulled from that study for analysis. LMM will be our primary analytic tool to investigate the association between genetic co-variants and treatment response in internet-based CBT. In the LMM, repeated measures of painrelated disability will be used as the dependent variable. The covariates include time, gene and demographic variables (e.g., sex) when necessary. In the initial evaluation, "genetic signatures" will be used as covariates. This approach markedly reduces complexity by combining known pathogenic variants in a class into an object such as "CFTR-related disorders", "Pathologic Trypsins", "Unfolded protein response (UPR)", "Lipotoxicity", "idiopathic" and "others" for etiology, as well as "opiate pharmacogenetics defect", "pain receptor" and others for modifiers. In addition, pathogenic variants with large effects (e.g. PRSS1 p.R122H, SPINK1 p.N34S) or high frequency (e.g. CTRC g.60G haplotype) will be evaluated as independent covariates. To investigate multiple genes and genetic signatures, we will conduct univariate gene analysis by regressing each gene independently on the pain-related disability outcome to see if there is reasonable signal of association between the gene and pain-related disability. Using this procedure, we screen out the genes with p value > 0.1. We then build

a multivariate model based on the genes with p value < 0.1 in the univariate analysis. In the case that the number of genes included in the multivariate model is still large, model selection (e.g., using LASSO) will be performed to obtain a parsimonious model and identify the genes that are significantly associated with the outcome pain-related disability. Further analysis utilizing machine learning programs for cluster analysis, such as principle component analysis, will be conducted as complementary and confirmatory analyses.

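### Pain-related disability is primary at two time points and tested three ways, with no Aim 1 test named as primary and no multiplicity control

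*Combined protocol and SAP*

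**What the plan says.** **Endpoint.** Section 3.1 reads "Primary endpoint is greater reductions in pain-related disability", with no time point, effect measure or test. Section 5.1 adds "Primary outcome is pain-related disability (T2, T3"), without ranking the two. The same section describes the later assessment as a check that gains are maintained.

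**Tests.** Section 14.1 lists three analyses of this outcome:

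- Levels, at baseline, 2 months and 6 months: "Two-sample t-test will be used to test the difference between the WebMAP group and WebED group in pain-related disability and other outcomes".
- Change, with no time point given: "The pre-post change in pain-related disability will also be assessed within and between groups using one-sample or two-sample t-test".
- A model with time, condition and their interaction: "Linear mixed models (LMM) will be further used to compare the change in pain-related disability over time".

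No significance level, order or alpha split is given there. The one analysis called primary belongs to Aim 2: "LMM will be our primary analytic tool to investigate the association between genetic co-variants and treatment response".

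**Size.** Section 10.4 says "the estimate of the standard deviation for the primary outcome pain-related disability is approximately 4", expects a difference of 1.5, and concludes "At the significance level of 0.05, we need 112 subjects per group to have 80% power to detect a difference". It does not say which time point the 1.5 refers to.

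**Missing data.** Section 14.1 promises intent-to-treat in all randomized subjects and says that the LMM copes with missing data. It does not say how the t-tests do.

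**The concern.** A confirmatory trial needs one answer to the question of which result decides efficacy. Here two time points and three kinds of test could each supply it, and they can disagree. A level difference at T2 may be significant while the change at T3 is not, or the reverse. Even the LMM leaves open whether the T2 contrast, the T3 contrast or the overall interaction decides.

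The designation could settle the trial's conclusion. Section 2.2 reports the earlier 273-adolescent trial's disability effect at p = 0.03. A result of that size passes at 0.05 and fails if 0.05 is split over two time points (0.025 each).

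The unspecified handling of missing data adds to this. With 10-15% attrition expected, the t-tests and the LMM may rest on different sets of children.

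**Working it through.** **1. Reproduce the plan's figure.** Inputs from section 10.4: difference 1.5, SD 4, alpha 0.05, power 80%. Sidedness is not stated; two-sided reproduces the figure.

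n per group = 2 (1.960 + 0.842)² × 4² / 1.5² = 2 × 7.849 × 16 / 2.25 = 111.6, so 112.

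One-sided testing would give 88. With 10% attrition 112 / 0.90 = 124.4, so 125; with 15% attrition 112 / 0.85 = 131.8, so 132. The planned 130 lies between. The sample size is right for one two-sided test.

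**2. Count the between-arm tests after baseline.** Levels at T2 and T3 (two), change at T2 and T3 on the widest reading (two), and the LMM time-by-condition test (one): five. If pre-post change means T1 to T2 only, there are four.

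**3. Familywise error under no effect.** Let D1, D2, D3 be the standardised arm differences at T1, T2, T3, with equal variances and a common within-child correlation r. The documents do not give r, so it is assumed to be 0.4 to 0.7.

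- Level test at visit k: Dk.
- Change test at visit k: (Dk − D1) / √(2 − 2r).
- LMM: 2-df chi-squared test on the two changes jointly.

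Each is judged at two-sided 0.05. The table gives the simulated probability of at least one positive (1,000,000 draws).

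| Tests counted | r = 0.4 | r = 0.5 | r = 0.6 | r = 0.7 |
|---|---|---|---|---|
| Levels T2, T3 | 9.3% | 9.1% | 8.8% | 8.3% |
| Levels, plus change at T2 | 13.1% | 13.0% | 12.8% | 12.5% |
| The same, plus LMM | 14.5% | 14.5% | 14.5% | 14.4% |
| Levels and change at T2, T3 | 16.1% | 16.1% | 16.1% | 15.9% |
| All five | 16.5% | 16.6% | 16.6% | 16.5% |
| Four t-tests, favouring WebMAP only (nominal 2.5%) | 8.2% | 8.2% | 8.1% | 8.1% |

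**4. Sensitivity.** A finite-sample run at 112 per arm and r = 0.5 gives 16.0% for the four t-tests and 16.5% for all five. Over 138 unequal correlation patterns (0.2 to 0.8) the five-test figure runs from 13.2% to 16.8%; with a linear-slope LMM it runs from 14.4% to 17.2%. Five independent tests would give 1 − 0.95⁵ = 22.6%, which overstates the risk because these tests are correlated.

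**5. Cost of two ways out.** One designated test at 0.05 leaves 112 per group and 80% power. Keeping T2 and T3 as co-primaries at 0.025 each needs 2 (2.241 + 0.842)² × 16 / 2.25 = 135.2, so 136 per group (152 to 160 enrolled per group at 10-15% attrition). At 112 per group, power at 0.025 falls to 71.4%.

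**The case against.** The strongest reply is that no passage says any single positive will be claimed as efficacy. A reader might infer a flat 16% error rate. The documents do not support that: it needs the any-positive rule, a 0.05 threshold for every test, and change tested at both T2 and T3. Section 14.1 states no threshold (0.05 appears only in the sizing) and mentions pre-post change without time points. This stands, so the size is given as a conditional range.

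Hypothesis 1 is also directional, and the two-sided figures count results favouring WebED, which could not support an efficacy claim. This stands too. In the relevant direction the rate is about 8%, though that is still roughly three times the nominal 2.5%.

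A reader might further infer that the t-tests will use observed cases only. The plan does not say so; it is silent on how they treat missing values.

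Two defences fail. It may be said that the LMM is plainly primary, but section 14.1 introduces it as an addition after the t-tests, and the sizing is for a two-group comparison of means. It may be said that T2 leads because T3 checks maintenance, but section 5.1 lists both as primary, and the disability result reported in section 2.2 is from baseline to 6 months.

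**Conclusion.** The concern holds. For Aim 1 the plan designates no primary test and no primary time point, and it has no multiplicity control, while the trial is sized for one comparison at 0.05. As written, nothing holds the efficacy conclusion at 5%.

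The size is conditional on each test being judged at 0.05 and any one positive being taken as efficacy. It then ranges from 8-9% (two level tests) to 16-17% (all five) two-sided, and is about 8% against 2.5% in the WebMAP direction for the four t-tests. The within-child correlation is assumed, but the result depends little on it.

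It does not follow that the sample size is wrong: 112 reproduces. Nor do the documents show that T3 must be the primary time point, since they give reasons for either.

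**What to change.** Before unblinding, state the same single primary test in sections 3.1, 5.1, 10.4 and 14.1:

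- the WebMAP minus WebED contrast in CALI-9 at one named time point;
- from one LMM with categorical time, prespecified unstructured covariance, age and sex;
- with baseline handled in one stated way, T1 either as a covariate or as part of the outcome vector, not both;
- at two-sided 0.05.

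Test the other time point only if the first is significant (fixed sequence). Label the t-tests supportive and state how they treat missing values.

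The sponsor chooses which time point comes first. The 6-month result in section 2.2 supports T3; the maintenance wording in section 5.1 supports T2. The timing of T3 must be reconciled before that choice: sections 5.1 and 5.4 place it six months after the intervention, whereas section 1.2 lists baseline, 2 months and 6 months. With a post-treatment visit at about 2 months, the first reading puts T3 at about 2 + 6 = 8 months from baseline.

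The cost is wording only. The 112 per group and 80% power stand, provided that the 1.5 difference and SD of 4 apply at the chosen time point, which section 10.4 should say. The downside is that the second time point alone can no longer carry the efficacy claim.

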5.2. Research procedures:⁹

Recruitment Study Procedure. 1) referral to the Web-MAP CP study by a collaborating INSPPIRE center or completion of community interest form, 2) telephone intake interview to determine study eligibility and explain study procedures, 3) coordinator will conduct informed consent over the phone and via secure REDCap link,

Study Procedure. 1) complete T1 (Baseline) study assessment via REDCap, 2) randomization to WebMAP or WebED program 3) phone instructional session for logging into the website and using the program. 4) participation in the randomized condition (see information table on each program), 5) complete T2 (about 2 months after baseline) via REDCap and 6) completing T3 6-month follow-up evaluation via REDCap.

Randomization Procedures. Using block randomization, children and parents will be randomized to two groups: WebMAP or WebED. Both groups will continue to receive standard medical care from a specialized pediatric pain clinic. We will generate a random numbers table using an online calculator to derive a randomization assignment in blocks of 4 for ID numbers.

WebMAP Group: The Web-MAP program teaches relaxation skills, pain coping strategies and parent behavioral and communication techniques to youth with chronic pain. Child participants will practice 8 skills. The skills included in Web-MAP are: 1) education about chronic pain and pain management, 2) recognizing stress and negative emotions, 3) relaxation and deep breathing, 4) implement coping skills at school, 5) cognitive skills, 6) lifestyle interventions, 7) staying active, and 8) relapse prevention. Parents will practice skills including: 1) education about chronic pain, 2) recognizing stress and negative emotions, 3) operant strategies I – attention and praise for positive coping, 4) operant strategies II –rewards for positive coping and reaching school goals, 5) modeling, 6) lifestyle, 7) communication, and 8) relapse prevention. Participants can also track daily activities and skills they used on the computer. Participants randomized to the WebMAP program will be practicing one of the 8 skills each week and will be contacted if they have not completed that skill after a week has passed. Mixed methods (email/text/phone calls if given permission by participant) will be used to contact participants to give reminders to continue logging into the program. Participants will receive their usual care and Web-MAP will not take the place of any aspect of their standard treatment

WebED Group. The purpose of the patient education control group is to control for time, attention, and computer usage. This group will serve as an attention control condition. Children will continue with the standard medical care that has been prescribed for their pain problem. Children and parents will be provided with access to a revised version of the Web-MAP study website, which will have two functional components: 1) information from publicly available educational websites about pediatric chronic pain management, 2) diary and assessments. This version of the website differs from the one accessed by the treatment condition in that it does not provide access to behavioral and cognitive skills training via treatment modules for children and parents.

During participation, a member of the study team would call/email/text to check in and to see if there are any problems or questions about using the program.

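### Fixed blocks of 4 tied to ID numbers, with no stated concealment or role separation: up to a third of allocations would be certain just before randomization if recruiting staff knew all earlier ones

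*Combined protocol and SAP*

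**What the plan says.** The allocation method is given in full under Randomization Procedures in Section 5.2. "We will generate a random numbers table using an online calculator", the text says, in order to "derive a randomization assignment in blocks of 4 for ID numbers". No second block size, stratification factor, list holder, concealment step or release rule appears there or elsewhere. The ratio is 1:1: Section 10.4 says "we will enroll 130 patients per group", and Section 5.1 gives the total of 260.

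The steps before assignment are a "telephone intake interview to determine study eligibility and explain study procedures", then consent by telephone with a coordinator, then "complete T1 (Baseline) study assessment via REDCap, 2) randomization to WebMAP or WebED program 3) phone instructional session". Sections 19.1 and 20.8.5 place screening and consent with the Seattle Children's team.

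After assignment, every family has a "phone instructional session for logging into the website and using the program". Also in Section 5.2, a study team member whose role is not named checks in during participation. WebMAP families work on one skill a week and "will be contacted if they have not completed that skill after a week has passed". WebED has no skill modules, so whoever sends that reminder knows the arm.

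Section 5.1 calls the trial double-blinded but does not say who is blinded.

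**The concern.** With one known block size and no stratification, the last place in every block is fixed by the first three, and the third is fixed when the first two match. Hiding the list does not prevent this if recruiting staff can see earlier assignments. Nothing in the plan keeps those assignments from them.

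The stake is selection before randomization. Eligibility in Sections 9.1 and 9.2 rests on reported pain episodes and on judgements such as whether pain is persistent or another systemic disease is severe. Section 10.3 expects 381 children to be screened for 260 enrolled. T1 must be completed before assignment, so a family can be lost between consent and randomization. Someone who could foresee the next arm could vary the effort made to keep that family, or the timing of its assignment. The intent-to-treat set in Section 14.1 is all randomized subjects and cannot repair selection that happened earlier.

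**Working it through.** **Inputs.** Block size 4 (Section 5.2); 1:1 allocation with 130 per group (Section 10.4); 260 children (Section 5.1); enrolment over about 3 years (Section 8.2). The plan gives no figure for predictability. Its sample size reproduces: 2 × (1.96 + 0.842)² × 4² / 1.5² = 111.6, so 112 per group, and 130 per group allows for 1 − 112/130 = 13.8% attrition. The present point leaves these figures unchanged.

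**1. Certain allocations, all earlier assignments known.** A 1:1 block of 4 has 6 equally likely sequences. In 2 of them the first two places match, which fixes the last two places. In the other 4 only the last place is fixed.

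- Per block: (2 × 2 + 4 × 1) / 6 = 1.333
- Share: 1.333 / 4 = 33.3%
- Over 260 / 4 = 65 blocks: 65 × 1.333 = 86.7, about 87 children

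**2. Best guess, all earlier assignments known.** The chance of a correct guess at places 1 to 4 is 1/2, 2/3, 2/3 and 1. The mean is 2.833 / 4 = 70.8%, against 50% without information.

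**3. Latest assignments not yet known.**

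- Latest one unknown: only place 4 can be fixed, and only when places 1 and 2 match (probability 1/3). The share is (1/3) / 4 = 8.3%, about 22 of 260.
- Latest two unknown: no place can be fixed, so 0%.

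**4. What this implies at consent.** 260 / (3 × 52.18 weeks) = 1.66 children per week. Assume Poisson arrivals, IDs issued at consent, and a fixed lag from consent to randomization. For a 1-week lag the mean number of unknown assignments is 1.66, and the certain share is e^(−1.66) × 0.3333 + 1.66 × e^(−1.66) × 0.0833 = 9.0%. For a 2-week lag it is 2.2%. The plan does not state the lag. The seven-day diary period in Section 5.3 makes about a week plausible.

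**5. Varying block sizes.** These were simulated over 400 trials of 260 children, each block size drawn with equal probability. The observer knows all past assignments and which sizes are possible, but not their order.

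- Fixed 4: 33.4% certain, 70.8% guessed correctly (agrees with steps 1 and 2)
- 4 and 6: 5.6% certain, 69% guessed correctly
- 4, 6 and 8: 2.3% certain (about 6 of 260), 68% guessed correctly

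Varying the sizes removes most of the certainty but little of the guessing advantage. An observer who cannot see past assignments is back at 50%.

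**The case against.** The strongest reply is that no text says recruiting staff learn past assignments. A coordinator is named for consent and an unspecified team member for check-ins. The trial is also described as double-blinded. This stands: exposure is plausible with one central team and WebMAP-only reminders, but it is inferred.

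A reader might also infer that a third of allocations are known before a child is enrolled. The documents do not support that. The footnote to Section 10.1 places enrolment at consent, and Section 5.2 places randomization after consent and T1. Earlier children may still be unassigned when the next one consents, which gives the lower figures in steps 3 and 4. The one-third figure belongs to the moment just before randomization, so influence on the intake decision is the least supported part.

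Two further readings go too far. The wording about ID numbers does not show that assignments are attached to IDs in advance, because the plan does not say when IDs are issued or whether the list is used in ID order. The log-in call is described for all participants and not as specific to an arm.

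Finally, Section 14.1 compares the arms at baseline and models change over time, so an imbalance in baseline disability would be visible and partly accounted for. That also stands, but it does not cover unmeasured prognostic differences.

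**Conclusion.** The point holds in conditional form. The plan fixes a single small block size and describes neither concealment nor separation of roles. If recruiting staff know the block size, the block boundaries and every earlier assignment, one third of allocations (about 87 of 260) are certain just before randomization and 70.8% can be guessed. That is the ceiling for inference from past assignments; it drops to 8.3% with one assignment outstanding and to 0% with two. If staff could read the list itself, every allocation would be knowable. The text neither says nor rules this out.

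The effect on the primary estimate cannot be sized from the documents, and self-reported outcomes do not in themselves create selection bias. Confidence is moderate because exposure is inferred. The change is still worth making because it costs very little.

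**What to change.** Replace the randomization sentence in Section 5.2 with text that provides for the following:

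- Someone with no role in recruitment generates a permuted-block list with randomly varying block sizes (for example 4, 6 and 8), which are not disclosed to recruiting staff.
- The list is loaded into REDCap. Each assignment is released singly, in order of randomization, and only after consent and T1 are complete.
- Where existing staffing allows, those who screen and consent do not handle the arm-specific contacts.
- The protocol states who holds the list and which parties are blinded.

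Varying the block sizes alone is not enough, as step 5 shows; concealed release and role separation carry most of the benefit.

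The cost is a few sentences and a set-up step in a system the trial already uses. If enrolment stops inside a block, the arms could differ by up to 4 children (half a block of 8) instead of 2 (half a block of 4). The sample size does not change.
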